### 3.3.3 Other Variables

Selected baseline variables described under outcomes ([Section 3.3.2.2](#)) will be assessed in the Step 1 analysis and will be used for controlling for confounding at baseline, through including the selected variables to the PS and matching OM-85 initiators to non-initiators (SOC/non-user group) using the PS. The following baseline variables will be considered in the PS:

- Patient demographics: Age and sex
- BMI
- RTI history, including type (Upper/Lower/Other) and number of previous RTI episodes
- Comedications
- Antibiotic prescriptions
- Selected comorbidities, especially smoking and respiratory conditions, such as asthma, COPD, and CB
- Overall and RTI-specific healthcare resource utilisation, especially duration of RTI-related hospitalisation(s) as a proxy for severity of prior RTIs
- Calendar year of CED

The confounders applied in the PS will be detailed in the SAP.

Variables used for defining sub-populations are described in [Section 3.2.2.3](#).

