**Figure 1 Study Design**

Note: CED: cohort entry date; RTI: respiratory tract infection; SOC: standard of care

-  For the patients who initiate OM-85 during the initiation grace period, another index date is assigned at the date of the 1st OM-85 prescription: OM-85 initiation date. This date is used as the index date in analyses on exclusively OM-85 initiators.
-  Outcomes defined for each objective are listed in [Table 7](#) and [Table 8](#).
-  Pregnancy at CED is estimated using a variable assessment window expanding from 183 days (6 months) before CED to 280 days (9 months) after CED, as detailed in [Section 3.2.2.3](#).
-  Selected covariates are defined during initiation grace period, to be used in sensitivity analysis for clone censor weighting.

period (see [Section 3.3.3](#)).

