- **CED:** The CED is defined during the inclusion period, as the date of the 2nd, 3rd, ... or nth RTI episode during the inclusion period (see inclusion criteria in [Section 3.2.2](#)). This is also the date when a patient fulfils all the eligibility criteria. The CED can occur any time during the inclusion period. If a patient meets the eligibility criteria more than once during the inclusion period, and thereby has several candidate CEDs, the CED used in the study will be selected at random, which is one of the unbiased methods of selection of index date (29). The CED defines the end of the baseline period and the start of the initiation grace period for each included patient.

- **Baseline period:** The baseline period for each included patient is defined as the time before the CED. The minimum baseline period will be 12 months, and the maximum baseline period will be as long as data are available in each country (from January 2005 in Belgium, from January 1994, for GPs and 2017 for paediatricians, in Italy, and from January 2018 in China). The minimum baseline period of 12 months will be used for assessing the RTI rate during the baseline period and other baseline variables ([Section 3.7.4.1](#)). The maximum baseline period (all available data) will be used for selected variables, such as comorbidities (e.g., allergies, myocardial infarction, and cancer, see [Table 8](#)), since these could have occurred earlier but may not have been recorded in the data during the 12-month baseline period. Extending the 12-month baseline period for such variables is expected to improve the accurate classification of them (i.e., decreases the risk of covariate misclassification).
- **Initiation grace period:** For each included patient, a 30-day initiation grace period starting from the CED will be applied, to allow the included patients to initiate OM-85 during a reasonable period after the CED, as it is unrealistic to expect that OM-85 would in clinical practice be prescribed on the date of meeting the eligibility criteria ([28,29](#)).
- **OM-85 initiation date:** The OM-85 initiation date will be the date of the first observed prescription of OM-85 during the 30-day initiation grace period, starting from the CED. This is applicable only for the OM-85 exposure group.

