**Table 4 Inclusion Criteria**

	Inclusion Criteria	Operational Definition
1	Patient aged $\geq 1$ year of age at CED	Aged $\geq 1$ year at CED
2	Patient has $\geq 1$ RTI episodes during the 12-month baseline period prior to CED	$\geq 1$ RTI episodes within a 12-month period during the inclusion period. The CED is the date of the 2 nd , 3 rd , ... or n th RTI episode (i.e., date of fulfilling the inclusion criteria). If one patient has multiple CED during the inclusion period, the CED will be selected randomly. The definition of an RTI episode provided in Section 3.3.2.1
3	Patient has $\geq 12$ months of continuous enrolment in the database prior to CED	$\geq 12$ months of continuous enrolment in the database prior to the CED. Operationally, patients were required to have entered the database at least 12 months before the CED to be included in the study. In THIN (Belgium and Italy), this can be defined by a district variable for entry to the database: first contact date. In Inspur (China), patients are required to have records in the database at least 12 months before the CED (during the 12-month baseline period) to be eligible for inclusion
4	No record of a prescription of any bacterial lysates in the 12-month baseline period prior to CED	No record of the country-specific drug codes ( Appendix 4 ) during the 12-month baseline period

Note: CED: cohort entry date; RTI: respiratory tract infection; THIN: The Health Improvement Network.

Inclusion criterion 2 on the requirement of having  $\geq 1$  prior RTI episodes is important to apply because OM-85 is indicated for prevention of recurrent RTIs (24). However, patients in the SOC/non-user comparator group may still have fewer prior recurrent RTIs than the OM-85 group receiving preventive therapy. Therefore, prior recurrent RTIs will also be used in the PS matching of the compared exposure groups. The impact (preventive effect) of OM-85 on the recurrence of RTIs is anticipated to be higher in patients with an increased recurrence risk (35). Hence, the analyses will also be stratified by the number of RTI episodes prior to CED (see [Table 5](#)).

The inclusion of patients is not defined by sex. Sex is instead defined at CED and considered in the PS.

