**Table 8 Secondary and Exploratory Outcomes**

Objective	Outcome	Definition	Measurement
Secondary objective 1  : Baseline characteristics	Sex	
 
Biological sex
 
	
 
Dichotomous variable (male/female)
 
Measurement at CED
 

	Age	
 
Age at index date
 
	
 
Categorical variable (1 to < 6 years, ≥ 6 to < 12 years, ≥ 12 to < 18 years, ≥ 18 to < 65 years and ≥ 65 years)
 
Measurement at CED
 

	BMI	
 
BMI = weight(kg)/height(m)
 
	
 
Continuous variable
 
Measurement closest to CED, during the 12-month baseline period
 

	Type and number of previous RTI episodes	
 
URTI only (e.g., acute nasopharyngitis, acute sinusitis, acute pharyngitis, acute tonsillitis)
 
LRTI only (e.g., whooping cough, pneumonia, acute bronchitis)
 
Other RTIs only: RTI not classified as upper or lower
 
Combination of URTI, LRTI, and/or Other RTIs
 
	
 
Categorical variable (diagnosis-related ICD-9/ICD-10 code, Appendix 3)
 
Continuous variable (number of URTIs, LRTIs, Other RTIs, URTI/LRTI/Other RTIs combined)
 
Measurement in the 12-month baseline period
 

	Comedications	
 
LABA, LAMA, ICS, LABA/ICS, LABA/LAMA, LABA/LAMA/ICS, antiallergic agents, leukotriene receptor antagonists, symptom relievers, systemic corticosteroids, systemic oral corticosteroids, influenza vaccines, influenza antivirals defined using country-specific drug codes (ATC, AIC, Other) (Appendix 4)
 
	
 
Binary variable (yes/no for each class of medication prescribed)
 
Continuous variable (number of prescriptions, length of treatment in days)
 
Measurement in the 12-month baseline period
 

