### 3.9.4 Time-Related Biases

Time-related biases were minimised by designing the study using the TTE framework (28,29). Importantly, follow-up was carefully selected to start at the end of the initiation grace period, equally for both exposure groups to eliminate immortal time bias. Starting follow-up at OM-85 initiation date for the OM-85 groups, and at CED for the SOC/non-user group would inevitably result in immortal time bias.

The initiation grace period was defined as 30 days, based on alignment with clinicians on a reasonable time for prescribers to prescribe preventive treatment with OM-85 after an RTI. Alternative grace periods may be considered in the SAP.

The time windows to detect the outcomes during the follow-up were chosen based on evidence from interventional studies on OM-85 with up to 12-month follow-up (24). In this study in real-world settings, follow-up was extended to 24 months, with the opportunity to investigate longer-term effectiveness and thereby complement the results of interventional studies. No bias is anticipated from this maximum 24-month window to detect outcomes.

The OM-85 treatment strategy was considered static (Section 3.3.1), based on its clinical use. However, in the static treatment strategy in the main analysis, OM-85 initiators will not be censored if/when they are prescribed other bacterial lysates during the follow-up. While this is consistent with the chosen treatment strategy, the time window for detecting the outcomes associated with OM-85 is not free from the effect of other bacterial lysates. Therefore, censoring follow-up at the first date of a prescription of another bacterial lysate will be applied in a sensitivity analysis, for both exposure groups.

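### The stated propensity-score windows end before the CED, so the type, setting and same-day treatment of the index RTI are not among the named covariates of the main matched comparison

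*Protocol*

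**What the plan says.** Section 3.3.3 builds the PS from "Selected baseline variables described under outcomes", meaning the variables of Table 8. The listed candidates include "RTI history, including type (Upper/Lower/Other) and number of previous RTI episodes", comedications, antibiotic prescriptions, and overall and RTI-specific healthcare use.

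Table 8 gives the same window for each of these rows: "Measurement in the 12-month baseline period". Section 3.2.1 defines that period: "The baseline period for each included patient is defined as the time before the CED". It adds: "The CED defines the end of the baseline period and the start of the initiation grace period for each included patient".

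The CED is the date of the 2nd, 3rd or nth RTI. Table 4 requires at least one earlier episode, counting "RTI episodes during the 12-month baseline period prior to CED". Section 3.9.4 explains that the 30-day grace period was set "based on alignment with clinicians on a reasonable time for prescribers to prescribe preventive treatment with OM-85 after an RTI".

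For covariates measured after the CED, a footnote to Figure 1 says: "Selected covariates are defined during initiation grace period, to be used in sensitivity analysis for clone censor weighting". Section 3.3.3 leaves the final PS list to the SAP, and Section 3.7.1 describes the candidate list as not exhaustive.

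**The concern.** The index RTI is the event after which the prescriber decides for or against OM-85. Its type, where it was treated and what was prescribed for it that day could influence both that decision and later RTI rates. A variable of that kind belongs in the PS. The windows for the relevant Table 8 rows stop just short of it.

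The main comparison relies on matching alone to control confounding. Section 3.9.1.2 calls confounding a particular challenge because there is no active comparator. The same section judges the success of matching from the descriptive baseline characteristics, whose RTI and treatment rows share the same windows. An imbalance in the index episode would therefore be neither adjusted for nor displayed.

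**Working it through.** The protocol gives no figure on this point. Table 9 concerns precision for primary objective 1 and does not bear on it. The check has two parts.

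**1. Which covariate windows reach the index episode?**

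| Covariate | Stated window | Covers the CED episode? |
|---|---|---|
| Age, sex | At the CED (Table 8) | Measured on that day, but not features of the episode |
| Calendar year | Year of the CED (3.3.3) | As above |
| Type and number of previous RTIs | 12-month baseline (Table 8) | No |
| Comedications, including corticosteroids | 12-month baseline (Table 8) | Not as stated |
| Antibiotics | 12-month baseline (Table 8) | Not as stated |
| Overall and RTI-specific healthcare use | 12-month baseline (Table 8) | Not as stated |
| Covariates in the grace period | After the CED (Figure 1 footnote, 3.7.7) | Sensitivity analysis only |

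For RTI type the exclusion is clear. At least one RTI must fall in the baseline before the CED, and the CED is the next or a later one, so the index episode is not a baseline episode. For same-day prescriptions and visits it follows from baseline being the time before the CED.

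The one severity proxy that Section 3.3.3 singles out, duration of RTI-related hospitalisation, refers to prior RTIs. A Table 8 footnote also says that the THIN databases do not cover hospital stays, so it cannot stand in for index severity in Belgium or Italy.

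**2. How large could the effect be?**

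The documents supply no inputs, so all of these are assumed:
- p0 = 0.30, the share of matched SOC patients whose index episode carries a given risk feature;
- p1 = 0.35 to 0.60, the same share in OM-85 patients, as it remains after matching;
- g = 1.1 to 2.0, the ratio by which the feature raises later RTI rates, equal in both groups.

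The average rate in a group is proportional to 1 + p(g − 1), so the IRR is multiplied by

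B = [1 + p1(g − 1)] / [1 + p0(g − 1)].

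| p1 | g = 1.1 | g = 1.25 | g = 1.5 | g = 2.0 |
|---|---|---|---|---|
| 0.35 | 1.005 | 1.012 | 1.022 | 1.038 |
| 0.40 | 1.010 | 1.023 | 1.043 | 1.077 |
| 0.50 | 1.019 | 1.047 | 1.087 | 1.154 |
| 0.60 | 1.029 | 1.070 | 1.130 | 1.231 |

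The corners are 1.035/1.03 = 1.005 and 1.60/1.30 = 1.231. If the feature is instead commoner in the SOC group by the same margins, the factors invert, to 1.03/1.035 = 0.995 and 1.30/1.60 = 0.813.

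**The case against.** **The SAP can settle it.** The PS list is expressly open, Section 3.7.1 adds clinical characteristics with no window, and the final confounders are deferred. A reader might infer that the protocol bars the index episode from the PS. It does not. What stands is narrower: the protocol fixes windows for the named variables, and a SAP that follows them literally would omit the index episode.

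**Day 0 may be covered elsewhere.** Figure 1, which summarises the windows, is not reproduced in the text available. Several sections speak of comparability or of the probability of OM-85 at the CED, and calling the CED the end of baseline does not say outright whether same-day prescriptions count. This leaves some doubt about same-day treatment. It leaves little about RTI type, given how episodes are counted.

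**Not every covariate precedes the CED.** That is correct: age, sex and calendar year are taken at it. The point is confined to RTI history, drugs and healthcare use.

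**The plan already has partial cover.** The clone-censor-weight sensitivity analysis starts at the CED and may use covariates measured after it, such as a new respiratory diagnosis or hospitalisation. Section 3.9.1.2 also admits residual confounding. Both are true, but the sensitivity analysis does not name index RTI type or treatment and does not alter the main matched estimate.

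**The size is conjecture.** This stands. A reader might infer an upward bias large enough to mask an IRR of 0.9. The protocol does not support that. It gives no share of lower RTIs by group and does not say that a lower RTI makes OM-85 more likely. Its 0.9 benchmark belongs to the precision calculation for primary objective 1. Matching on prior RTI type and count, antibiotics and respiratory disease would probably absorb part of any crude difference; with 5 points remaining, the factor is only 1.005 to 1.038.

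**Conclusion.** The concern holds in a limited form. On the protocol's own definitions, the type, setting and same-day treatment of the index RTI fall outside the stated windows for the RTI, drug and healthcare-use covariates in the main PS-matched analysis of primary objective 2. This may leave confounding by indication that the planned balance tables would not show.

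The size and direction cannot be derived from the document. The range of about 1.005 to 1.23 on the IRR, reversible in direction, rests wholly on the assumed shares and rate ratios and on those imbalances surviving the match. The conclusion about the windows needs none of those assumptions. It rests on the text of Sections 3.2.1 and 3.3.3 and Tables 4 and 8, with the reservation about Figure 1.

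**What to change.** In Section 3.3.3 and Table 8, or in the SAP with a cross-reference:

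- State that the covariate window for the PS includes day 0, the CED.
- Add the type of the CED episode (upper, lower, other) as its own covariate, separate from the history of previous episodes.
- Add the antibiotic and the systemic corticosteroid prescribed on the CED.
- Add care setting at the CED for Inspur.
- Report the balance of these variables before and after matching, alongside the other baseline characteristics.

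For the PS, the window should stop at day 0. Running it on into the grace period would bring in events that follow OM-85 initiation in some patients.

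The cost is wording and a few more rows in the balance table. The CED is defined from a coded RTI diagnosis, so its type is already known, and antibiotics and systemic corticosteroids are already study variables drawn from prescription records. No new data collection is needed.

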## **3.4 Data Sources**

The feasibility assessment was conducted to select the most appropriate and fit-for-purpose data sources for this study. The data sources were selected based on the covered geography, the covered settings of care with particular focus on the capture of primary care, the potential numbers of patients available considering preliminary inclusion criteria, coverage and completeness of variables of interest to address the study objectives, as well as operational considerations such as data access process and timelines. The data sources were requested to quantify the availability of the data elements. The availability of variables was completed for all data sources. According to the feasibility assessment, the data sources described below were the most applicable and will therefore be used as data sources in this study. These data sources are used for defining all variables of the study, including inclusion criteria, variables that will end follow-up, sub-populations, exposures, outcomes, and other variables.

### **3.4.1 The Health Improvement Network: Belgium and Italy**

THIN® is a large European database of fully anonymised, non-linkable and non-extrapolated Electronic Health Records collected at the physicians' level. These anonymised patient-level data are obtained from a network of voluntary physicians. In Belgium and Italy, no ethics submission is needed for the current study. An ethics submission to access data from THIN is mandated in case study results will be published. In such case, THIN will submit an ethical application via the THIN Euroboard.

THIN Belgium covers information from GPs and has information on > 500,000 patients per year, with an average follow-up of 9 years. THIN Italy covers information from GPs and has information on > 550,000 patients per year, with an average follow-up of 7 years. The feasibility assessment found that overall, the variables required to address the primary objectives are well captured and of good completeness in both THIN Belgium and THIN Italy, with the exceptions of vaccine administration, lung function tests, and hospitalisation data. Lung function data will therefore not be collected, and vaccination data will be limited to influenza vaccinations. As information is collected from GPs only, the information on healthcare resource utilisation is not complete. Date of birth is captured as year of birth and therefore age in the first year of life cannot be assessed with further granularity than this.

### **3.4.2 Inspur: China**

Inspur is a government-owned company and is authorised to manage city-level data in the Tianjin city of China, which is a large northern city. The database includes Electronic Medical Record (EMR) data, at the patient level, from 82 public hospitals in Tianjin, including secondary and tertiary hospitals in Tianjin city. Secondary hospitals in China are mid-sized regional facilities with 100 to 500 beds, serving district or county levels, while tertiary hospitals are larger, comprehensive medical centres with over 500 beds, offering more specialised services, advanced technology, and typically serving city, provincial, or national populations. Compared to other

databases in China which cover only tertiary hospitals, Inspur collects regional data from secondary and tertiary hospitals, which increases the representativeness of the Chinese population. The database links EMR data, laboratory data and image data, however, the data are not linkable to other sources outside of the Inspur network. It is noteworthy that only one ethics committee (EC)/IRB is needed for the Inspur database rather than needing each hospital's approval, which facilitates the EC/IRB process. Although the time frame covered in Inspur starts from 2005, reliable data electronic collection/coverage spans from January 2018 to latest available data, which were therefore used for the study period time frame. The feasibility assessment found that most of the variables required for the study are captured with good completeness in the Inspur database, with the exceptions of vaccine administration and lung function tests. These data will therefore not be collected and analysed from Inspur as part of this study. Furthermore, the feasibility counts of patients treated with OM-85 revealed that the majority are children under 11 years of age; however, the adult population remains significant in size (utilising preliminary inclusion and exclusion criteria).

### 3.5 Study Size

In this non-interventional study, all patients available in the databases will be included in the study population. Based on the feasibility assessment, 14,362 patients meeting inclusion criteria and using OM-85 are available in Belgium (of which 10,555 patients aged  $\geq 18$  years old), 3,219 patients in Italy (of which 2,742 patients aged  $\geq 18$  years old), and 8,656 patients in China (of which 1,338 patients aged  $\geq 18$  years old). The study size is based on including the maximum number of patients for the OM-85 group. However, the strategy to include patients to this study using the TTE framework is not identical to the feasibility assessment, and fewer OM-85 exposed patients will be included in this full study using the TTE framework ([Section 3.9.5](#)).

For primary objective 1, the study size required to estimate the difference between rates of two groups (pre- and post- OM-85 treatment) is evaluated based on the precision of the point estimate, as described below.

The CI for point estimate of incidence rate ratio (IRR) is calculated as follows ([38](#)), where a and b are the counts of events in each group, PT1 and PT2 are the person-time (in person-years [PYs]) in each group, and F is a quantile of the F distribution.

$$\widehat{\text{IRR}} \text{ CI} = \left( \frac{PT_2}{PT_1} \right) \left( \frac{a}{b+1} \right) \frac{1}{F_{\alpha/2, 2(b+1), 2a}} \text{ to } \left( \frac{PT_2}{PT_1} \right) \left( \frac{a+1}{b} \right) F_{\alpha/2, 2(a+1), 2b}$$

With a hypothetical population rate of 2 episodes per person per year in the baseline (based on reported Upper RTI global age-standardised incidence rate of 225,505 per 100,000 person-years, in the Global Burden of Diseases, Injuries, and Risk Factors Study [GBD] 2019 ([39](#))), and assuming equal person-time in the two groups, the width of the 95% CI for the estimated IRR under difference effect sizes and sample sizes are demonstrated in [Table 9](#).

